After Cycle 1 and Cycle 2, which will only occur if needed, of usability testing are complete, we will email all study participants a link to the final NDR tool. If Cycle 3 is needed, participants will run through the NDR tool independently and then fill out an online survey hosted on REDCap. This survey will include a modified version of the USE Scale (a measure of usefulness, satisfaction, ease of use, and ease of learning) to measure the participant's final satisfaction with the tool. Additionally, we will ask participants to complete a brief, semi-structured interview over the phone to assess the overall NDR tool's acceptability, satisfaction, and overall impressions. This semi-structured interview will help enhance the quantitative data collected in Cycle 3.

Aim 2: All study timepoints will take place online (REDCap survey) with the exception of the study screener (phone) and e-CONSENT (participant will view online while research study coordinator is on the phone).

Baseline Survey 1: Participants who consent to participate in the study will be sent a link to the REDCap Baseline Survey 1 to their email address. The Research Study Coordinator will confirm that the Baseline Survey 1 link was received while they are still on the call with the participant after the e-Consent to ensure it was sent to the correct email address, was not in a Spam/Junk folder, etc. Participants will have 7 days to submit their completed Baseline Survey 1.

Anticipated participant time required to complete Survey 1: 35 minutes

Study Intervention - Assigned NDR Exercises: Once the completed Baseline Survey 1 is received from the study participant, the Research Study Coordinator will send them a unique study link which includes their embedded randomization assignment (pre-randomized) to their email. The link will give participants access to the study website, www.NegotiAge.com, as well as the negotiation platform where they will access their assigned NDR exercises, IAGO. Participants will have 14 days to complete their assigned exercises.

Anticipated participant time required to complete Study Intervention – Assigned NDR Exercises*: 10-30 minutes

*Participants will be randomized to which/how many negotiation activities they are required to do so we are providing a range of time.

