Post-Intervention Survey 2: Once a participant has completed all of their assigned NDR exercises, the research study team will be able to access their completion status via an automated report. Participants who have completed all of their assigned study activities will be emailed a link for them to complete the Post-Intervention Survey 2 on the REDCap survey platform. Participants are expected complete the Post-Intervention Survey 2 within 7 days of completing all of the Assigned NDR Exercises.

Anticipated participant time required to complete Survey 2: 25 minutes

1-Month Post-Intervention Survey 3: Study participants will be emailed a link to Survey 3 which will be hosted on REDCap and is to be completed online. Participants will be sent this survey for completion one-month after completion of Survey 2. Participants are expected to complete the 1-Month Post-Intervention Survey 3 within ± 14 days of being sent the survey link. If a participant misses either of the follow-up surveys (Survey 3 and/or Survey 4), they will continue to be enrolled in the study.

Anticipated participant time required to complete Survey 3: 25 minutes

3-Month Post-Intervention Survey 4: Study participants will be emailed a link to Survey 4 which will be hosted on REDCap and is to be completed online. This is the final study activity. Participants will be sent this survey for completion three-months after completion of Survey 2. Participants are expected to complete the 3-Month Post-Intervention Survey 3 within ± 14 days of being sent the survey link.

Anticipated participant time required to complete Survey 4: 30 minutes

Data collection instruments by time-point listed below:

Data Collection Instrument	Consent (1)	Enrollment (2)	Survey 1 - Baseline (3)	Survey 2 - Post-Intervention (4)	Survey 3 - 1-Month (5)	Survey 4 - 3-Month (6)
e-Consent (survey)	✓					
Post-Consent - Survey 1 Instructions		✓				
Participant Contact Information		✓				
Participant Communication Log		✓				
Screener	✓					
Enrollment Status	✓					
Study Completion Compliance	✓					
Gift Cards - Survey 1		✓				
Gift Cards - Survey 2		✓				
Gift Cards - Survey 3		✓				
Gift Cards - Survey 4	✓					
Positive Affect & Wellbeing (survey)			↓		↓	↓
PROMIS SF - Anxiety (survey)			↓		↓	↓
Caregiver Burden - Zarit (survey)			↓		↓	↓
Neuro-QoL Caregiver SF - TBI-CareQOL Caregiver-Specific Anxiety (survey)			↓		↓	↓
PROMIS SF - Fatigue (survey)			↓		↓	↓
PROMIS SF - Emotional Support (survey)			↓		↓	↓

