12.0 Waivers and Alterations of Consent Information: N/A

13.0 Financial Compensation:

Aim 1: We will compensate study participants for their time and the amount of the compensation will depend on which study activities they complete. We anticipate that the study participants will spend up to 8 hours on the usability testing (approximately 2-3 hours per each cycle). Subjects will be compensated only for the study activities they complete. Compensation was determined by using a rate of \$50/hour for each activity.

Activity	Estimated Duration	Visa Gift Card Value
Cycle 1: Initial usability testing of NDR Tool	Up to 3 hours	\$150
Cycle 2 (if needed): Usability testing of NDR Tool refinements	Up to 2 hours	\$100
Cycle 3 (if needed): Final usability testing		
Survey 3a. Final review & REDCap survey	Up to 2 hours	\$100
Survey 3b. Semi-structured phone interview.	Up to 1 hour	\$50
TOTAL	Up to 8 hours	Up to \$400

We will compensate research study participants with Visa gift cards. They will receive compensation within 4 weeks of their completion of the study activities. Since the study activities are completed remotely, the Visa gift cards will be mailed to study participants at their specified mailing address. Participants will be compensated the full amount even if they do not spend the estimated duration period on the activity (e.g. if a participant only spends 2 hours on Cycle 1, they will be compensated \$150, not \$100).

We will not compensate study participants for study activities they do not complete. However, they will still be allowed to participate in Aim 1 of the study if they do not complete all three activity cycles (e.g. if they only complete Cycle 1 but not Cycle 2, they are still eligible to complete Cycle 3). Participants will not incur any costs in participating in this research study.

Aim 2: All enrolled participants will be compensated for their time and effort for the completion of each activity in Aim 2. Participants will receive up to \$500 in virtual Visa gift cards. Participants will only receive compensation for the activities that they complete. However, participants will still be allowed to continue their participation in the study even if they do not complete all the study activities. All activities will be completed online and the corresponding compensation upon completion is listed below:

Activity, by time-point	Estimated Duration	Virtual Visa Gift Card Compensation Amount
Baseline: Survey 1	Up to 35 minutes	\$25

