Confidentiality may be broken by research staff to ensure the study participant's safety if there is an imminent threat to self or others. All these potential losses of confidentiality are disclosed in the consent documents. All potential risks associated with participation in this study are disclosed in consent documents. The procedures to protect against risks associated with potential loss of confidentiality include keeping participant data strictly confidential, except as mandated by law.

Procedures to protect against risk associated with experiencing emotional discomfort in answering survey questions and/or completing conflict activities include information participants that they can decline to answer any questions they choose. Likewise, they will be informed that they do not have to complete any negotiation activities that they choose not to. Negotiation and dispute resolution training programs generally have not been shown to cause any harm. Participants can elect to stop the training activities at any time. Participants will give voluntary responses to survey questions; they can decline to answer any questions that they choose when they are completing the study surveys online.

We will inform participants that their involvement in the study is voluntary, and they may withdraw from the study at any time. We do not anticipate any circumstances where a participant would be withdrawn from the research without their consent.

17.0 Provisions to Protect Participant Privacy and Data Confidentiality:

Aim 1:

Participant Privacy. In all research documentation, a unique identification number (“Study ID”) will identify participants, not by name, and any other identifying information (e.g. personal and/or contact information) will be kept separate from the other data; all information will be kept in secure, password protected files. This also includes Zoom video and audio files for those participants in Aim 1. We will ask participants to try and refrain from using any identifiers during recorded sessions. Further, unless required by law, only the study investigators, members of the research project staff, and representatives of the Northwestern University will have the authority to review any study records. In such case, they too will be required to maintain confidentiality.

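### Caregivers who never finish their assigned exercises, or never return Survey 2, have no scheduled post-baseline measurement of the primary outcome, which does not fit the intent-to-treat analysis

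*Protocol*

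**What the plan says.** **Schedule (Protocol 7.0, Aim 2).** Once the baseline survey is in, each participant is sent a link carrying the randomised assignment. "Participants will have 14 days to complete their assigned exercises". An automated report then shows who has finished, and "Participants who have completed all of their assigned study activities will be emailed a link for them to complete the Post-Intervention Survey 2". The expected return is stated: "Participants are expected complete the Post-Intervention Survey 2 within 7 days of completing all of the Assigned NDR Exercises". For Survey 3, "Participants will be sent this survey for completion one-month after completion of Survey 2"; for Survey 4, "Participants will be sent this survey for completion three-months after completion of Survey 2". One rule covers missed surveys: "If a participant misses either of the follow-up surveys (Survey 3 and/or Survey 4), they will continue to be enrolled in the study".

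**Primary outcome.** The instrument table in Protocol 7.0 marks Positive Affect and Well-Being at Surveys 1, 3 and 4, with nothing at Survey 2. SAP Table 3 agrees (months 0, 1 and 3).

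**People who do not finish.** Protocol 16.0 (Aim 2) provides for them: "they will be informed that they do not have to complete any negotiation activities that they choose not to". Protocol 13.0 (Aim 2) keeps them in: "participants will still be allowed to continue their participation in the study even if they do not complete all the study activities". The SAP paragraph on minimising loss to follow-up says follow-up continues after treatment drop-out.

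**Analysis.** The SAP's quantitative section plans intent-to-treat linear mixed models, with component-by-time terms for change from baseline to 1 month. Its power section says the resulting effect sizes will decide which components are kept and will power the next trial.

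**The concern.** The rules form a chain: finish every exercise, then receive Survey 2, then return it, and only then acquire dates for Surveys 3 and 4. A participant who never completes the first or third step has no scheduled post-baseline primary outcome. One unreturned survey that does not carry the primary outcome removes the dates of the two that do.

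Such people would enter the mixed model with a baseline value only. The component effects would then rest on those who finished and returned Survey 2, and on a missing-at-random assumption that the SAP does not state. The estimates would lean toward the effect of doing an exercise rather than of being assigned it.

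The loss could also differ by component, because the number of exercises is itself randomised. An outcome that was never requested cannot be recovered at the analysis stage.

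**Working it through.** **1. The plan's own figure.** The SAP states d = 0.65 at 80% power with 40 per component group, two-sided 5%. A noncentral t calculation gives 81.9%, and 0.65 × 6 = 3.9 points, as stated. The GEE-based run cannot be repeated because its working correlation is not given. The point here does not depend on it.

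**2. Is there another date for these people?**
- The missed-survey rule in Protocol 7.0 covers Surveys 3 and 4 only.
- Protocol 13.0 and the SAP's loss-to-follow-up paragraph state an intention but no trigger.
- The SAP's Survey Time Points paragraph speaks of contact at 1 and 3 months, but names no start date and follows a sentence about what happens once training is complete.

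None of them supplies a date.

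**3. Assigned load.** From SAP Table 1, conditions 1 to 8 carry 1, 2, 2, 3, 2, 3, 3 and 4 exercises. For any component the mean is 3 on the Yes side and 2 on the No side.

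**4. Size of the gap (assumption).** Protocol 3.0 recruits up to 150 until 120 complete all Aim 2 activities; the SAP plans to enrol 130. The shortfall is 10/130 = 7.7% to 30/150 = 20%. It includes missed surveys, and 150 is a ceiling, so charging all of it to the exercises is an upper illustration.

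**5. Independent skipping, probability p per exercise.**
- Overall completion = (1−p)(1−p/2)³; Yes side = (1−p)²(1−p/2)²; No side = (1−p)(1−p/2)².
- Overall = 120/130 gives p = 0.032: Yes 0.908, No 0.938, so 6.0 against 4.0 lost of 65 each.
- Overall = 120/150 gives p = 0.087: Yes 0.764, No 0.836, so 17.7 against 12.3 lost of 75 each.
- If a skipped exercise forfeits its effect, the assigned effect is (1−p) times the effect in finishers. Overstatement is 1/(1−p) = 1.03 and 1.09. At 0.65 SD and SD 6 this is 0.65 × p × 6 = 0.12 and 0.34 points.

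**6. All-or-none non-completion, probability q.** Overstatement is 1/(1−q) = 1.08 at 7.7% and 1.25 at 20%. In points, 0.65 × q × 6 = 0.30 and 0.78. Loss does not differ by component in this case.

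**7. Does keeping baseline-only people in the model remove this?** No. In a simulated component-by-time model with a random intercept (2,000,000 participants, correlation 0.6, effect 0.65 SD if the exercise is done), following everyone gave 0.631 SD at p = 0.032 and 0.595 at p = 0.087. Baseline for all plus finishers' follow-up gave 0.651 at both. The ratios, 1.03 and 1.09, match step 5.

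**8. Selection.** If non-finishers' change differs by 0.5 SD (assumed), bias is 0.5 × (No − Yes) = 0.015 and 0.036 SD, or 0.09 and 0.22 points. Its sign depends on the direction of that difference.

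**9. Yardstick.** The 95% half-width for a 60 v 60 main effect on change is 1.96 × 6 × √(2(1−r)) × √(2/60) = 2.1 points at r = 0.5 and 1.7 at r = 0.7 (r assumed).

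**10. Survey 2 non-return.** If the SAP's follow-up adherence of more than 90% is applied to Survey 2 alone, fewer than 13 of 130 would lose both dates. The standard error would rise by up to 1/√0.9 = 1.05.

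**The case against.** The strongest reply is that the documents plainly mean to follow everyone. Protocol 13.0 and the SAP's loss-to-follow-up paragraph say so, and staff may well send the surveys anyway. The manual of operating procedures mentioned in Protocol 18.0 may set a date, but it is not among the documents. The intention stands; it shows what the schedule ought to deliver. It does not supply the missing date, and the Protocol's anchor for Surveys 3 and 4 is explicit.

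Four further points have force:
- **Day 14.** A reader might infer that anyone unfinished at day 14 is lost. The documents do not support that: nothing closes access or cancels the Survey 2 trigger then. Someone who finishes on day 20 still gets Survey 2 and, on returning it, dates for Surveys 3 and 4. A late Survey 2 works the same way.
- **The analysis.** A reader might infer that the intent-to-treat analysis cannot be run. It can, because a mixed model keeps people with baseline data only. What changes is what the estimate rests on.
- **The rate.** The 120 comes from the Protocol and the 130 from the SAP; neither document offers the ratio as attrition. The exercises take 10 to 30 minutes, and $300 of the $500 compensation is tied to them plus Survey 2, so non-completion may well be low.
- **The direction.** Overstatement requires that skipped exercises forfeit their benefit. The documents do not say so; it is an assumption.

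**Conclusion.** The point holds for participants who never finish the exercises and for those who never return Survey 2. Followed as written, the schedule gives them no post-baseline primary outcome, and this does not fit the intent-to-treat analysis or the stated follow-up of people who stop.

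The likely bias is small. Under the assumptions in the working, overstatement runs from 1.03 to 1.09 with independent skipping and from 1.08 to 1.25 with all-or-none non-completion, together about 0.1 to 0.8 points. That is below the half-width of 1.7 to 2.1 points and the 3.9-point detectable difference. The true figure is probably nearer the low end, because the shortfall used also contains missed surveys.

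A reader might infer that the wrong components would be retained. The documents do not support that: under these simple models the overstatement is the same for all three, so it would not by itself change their ranking. The change is still worth making, because the effect sizes feed the next trial and the remedy is cheap.

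**What to change.** Date Surveys 3 and 4, for every participant sent an assignment link, from exercise completion or close of the 14-day window, whichever is first, whether or not Survey 2 is returned. Bring Protocol 7.0 and 13.0 and the SAP's Survey Time Points, quantitative analysis and loss-to-follow-up text into line with this. State in the SAP the missing-data assumption for values that are still absent.

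Keep Survey 2 triggered by exercise completion. Sending it at window close would take its knowledge, conflict-handling and utilisation measures before late finishers had completed the intervention.

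**Cost.** Changed email triggers and a protocol amendment. For people who finish within 14 days and return Survey 2 on time, Surveys 3 and 4 move at most 7 days earlier, inside the ±14-day window; for later finishers or returners the shift can be larger. Added payments are $75 + $100 = $175 per extra person followed: $1,750 for 10 people and $5,250 for 30. Estimated effects may come out slightly smaller.

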9.0 Incomplete Disclosure or Deception: N/A

10.0 Consent Process

Aim 1: Informed consent (electronic) will be obtained by Northwestern research study coordinator using the REDCap e-consent application after the participant is deemed eligible to participate after completing the study screener. Informed consent will be viewed as a process, i.e., at several times during review of the IRB approved consent document, the participant will be asked to explain in his/her own words what his/her understanding of the consent. This will enable the research personnel to enter into a dialogue with the participant and ensure that the participants understands that he/she is free to withdraw at any time without penalty. We will provide information to the participants in terms that they can fully understand. There will be no exertion of any overt or covert coercion. The e-consent document is written in language that the potential participant can understand, and they will be encouraged to ask questions prior to giving consent.

A copy of the signed e-consent form will be downloaded from REDCap and uploaded into Study Tracker as well as saved on the FSMResFile shared project folder. All study participants will receive a copy of the signed e-consent form via email to their preferred email address.

Aim 2: Research study coordinators using the REDCap electronic (e-consent) application will obtain informed consent. If the individual is eligible and is interested in participating, they will be sent a link to the electronic-consent form (e-consent) to their preferred email address. The Research Study Coordinator will explain the study to the participant over the phone, and both the participant and research coordinator will go through the e-consent together.

If the participant does NOT have time to complete the e-consent after the screening assessment and/or does not have access to view/sign the e-consent that day, the Research Study Coordinator will schedule a day/time for completion of the e-consent with the participant. If the participant agrees to participate, they will sign the consent form electronically. The research staffer will also sign and date the form electronically.

Informed consent will be viewed as a process, i.e., at several times during review of the IRB approved consent document, the participant will be asked to explain in his/her own words what his/her understanding of the consent. This will enable the research personnel to enter into a dialogue with the participant and ensure that the participants understands that he/she is free to withdraw at any time without penalty. We will provide information to the participants in terms that they can fully understand. There will be no exertion of any overt or covert coercion. The e-consent document is written in language that the potential participant can understand, and they will be encouraged to ask questions prior to giving consent.

A copy of the signed e-consent form will be downloaded from REDCap and uploaded into StudyTracker as well as saved on the project's secured shared drive folder. All study

participants will receive a copy of the signed e-consent form to their preferred email address.

11.0 Waiver of Participant Signature on Consent Form: N/A

We are not requesting a waiver of participant signature on the consent form since signature will be obtained remotely using the REDCap platform for both study Aims 1 and 2.

12.0 Waivers and Alterations of Consent Information: N/A

13.0 Financial Compensation:

Aim 1: We will compensate study participants for their time and the amount of the compensation will depend on which study activities they complete. We anticipate that the study participants will spend up to 8 hours on the usability testing (approximately 2-3 hours per each cycle). Subjects will be compensated only for the study activities they complete. Compensation was determined by using a rate of \$50/hour for each activity.

Activity	Estimated Duration	Visa Gift Card Value
Cycle 1: Initial usability testing of NDR Tool	Up to 3 hours	\$150
Cycle 2 (if needed): Usability testing of NDR Tool refinements	Up to 2 hours	\$100
Cycle 3 (if needed): Final usability testing		
Survey 3a. Final review & REDCap survey	Up to 2 hours	\$100
Survey 3b. Semi-structured phone interview.	Up to 1 hour	\$50
TOTAL	Up to 8 hours	Up to \$400

We will compensate research study participants with Visa gift cards. They will receive compensation within 4 weeks of their completion of the study activities. Since the study activities are completed remotely, the Visa gift cards will be mailed to study participants at their specified mailing address. Participants will be compensated the full amount even if they do not spend the estimated duration period on the activity (e.g. if a participant only spends 2 hours on Cycle 1, they will be compensated \$150, not \$100).

We will not compensate study participants for study activities they do not complete. However, they will still be allowed to participate in Aim 1 of the study if they do not complete all three activity cycles (e.g. if they only complete Cycle 1 but not Cycle 2, they are still eligible to complete Cycle 3). Participants will not incur any costs in participating in this research study.

Aim 2: All enrolled participants will be compensated for their time and effort for the completion of each activity in Aim 2. Participants will receive up to \$500 in virtual Visa gift cards. Participants will only receive compensation for the activities that they complete. However, participants will still be allowed to continue their participation in the study even if they do not complete all the study activities. All activities will be completed online and the corresponding compensation upon completion is listed below:

Activity, by time-point	Estimated Duration	Virtual Visa Gift Card Compensation Amount
Baseline: Survey 1	Up to 35 minutes	\$25
Immediate-Post Intervention*: Survey 2	Up to 60 minutes	\$300
1-Month Post Intervention: Survey 3	Up to 25 minutes	\$75
3-Months Post Intervention: Survey 4	Up to 30 minutes	\$100
TOTAL		\$500

*Includes completion of Study Intervention - Assigned NDR Exercises in addition to Survey 2

Virtual Visa gift cards will be emailed to study participants upon completion of each study activity no later than 5 days after each activity completion. The research study coordinator will call or email participation to confirm receipt of the virtual gift card and log all compensation mailings on the Aim 2 Participant Compensation Log. Participants will not incur any costs in participating in this research study.

We are not able to receive a signed receipt from the study participants for either Aim 1 or Aim 2 given that these study activities will take place virtually. The Research Study Coordinator will sign and date a receipt including the study participant ID and date of survey completion along with the compensation amount. This receipt will be kept electronically on the shared drive. In addition, a compensation tracking log will be tracked in Excel which will include the following fields: study ID, type of survey/activity completed, date survey/activity completed, Visa gift card number, ICN number, date gift card mailed, value of gift card, and the initials of the Research Study Coordinator who emailed the compensation.

